#### 9.4.2 **Safety analyses**

The summary of safety results will be presented by treatment group. All safety analyses will be performed on the Safety Population. The baseline value is defined generally as the last available value before randomization. The treatment emergent adverse event (TEAE) period is defined as the time between the first administration of study medication to the last administration of the IMP + 98 days.

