AESI and other AE groupings	
Incidence of each type of AESI and other AE groupings will be tabulated by treatment group. For each type of AESI, the following analysis will be generated.
 
 
- A summary of the number (%) of patients with 
 
• any TEAE
 
• any SAE (regardless of treatment-emergent status)
 
• any treatment-emergent SAE
 
• any AE leading to death
 
• any TEAE leading to death
 
• any TEAE leading permanent treatment discontinuation
 
• any TEAE related to IMP reported by investigator
 
• Number of patients with the TEAE per 100 patient-years
 
• any TEAE by maximum intensity, corrective treatment, and final outcome
 
 
 
- Kaplan-Meier (K-M) estimates of probability of having at least one TEAE at specific time points, and K-M curve to depict the course of event onset over time.
 
 
The method to identify AESIs and other AE groupings will be specified in the SAP.

Death	
The following deaths summaries will be generated:
 
 
- Number (%) of patients who died by study period (TEAE, on-study) summarized on the safety population by treatment received
 
- Death in nonrandomized patients or randomized and not treated patients
 
 
Treatment-emergent AE leading to death (death as an outcome on the AE eCRF page as reported by the Investigator) by primary SOC, HLGT, HLT, and PT showing number (%) of patients sorted by internationally agreed order of SOC and alphabetic order of HLGT, HLT, and PT.

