2.1.4 Safety endpoints

The safety analysis will be based on the reported adverse events and other safety information, such as clinical laboratory data, vital signs, ECG and physical examination.

Observation period

The observation period will be divided into 4 epochs:

- The **screening** epoch is defined as the time from the signed informed consent date up to the time prior to first administration of the IMP.
- The **treatment** epoch is defined as the time from the first administration of the IMP to the last administration of the IMP + 14 days.
- The **residual treatment** epoch is defined as the time from the last administration of the IMP +15 days to the last administration of the IMP + 98 days.

The treatment-emergent adverse event period will include both **treatment** and **residual treatment** epochs.

- The **posttreatment** epoch is defined as the period of time starting the day after the end of the treatment-emergent adverse event period up to the end of the study (defined as last

protocol planned visit or the resolution/stabilization of all serious adverse events and adverse events with pre-specified monitoring).

- The on-study observation period is defined as the time from start of treatment until the end of the study (defined as last protocol planned visit or lost to follow-up or the resolution/stabilization of all serious adverse events and adverse events with pre-specified monitoring).

Safety events adjudication

Adjudication will be performed by experts independent of sponsor for the evaluation of whether deaths, cardiovascular SAEs and respiratory SAEs meet criteria for cardiovascular assessment endpoints. A confirmatory adjudication will occur for AECOPD exacerbations. Adjudicators will adjudicate these events in a consistent and unbiased manner throughout the study.

The goal of the adjudication is to ensure that all events reported by the site are judged uniformly, using pre-specified criteria by a group independent of the Sponsor. Adjudication Committee members will be blinded to treatment allocation. Adjudication Committee members' responsibilities and the process for data review are described in the AC Charter/Manual of Operation.

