2.4.3.1 Extent of investigational medicinal product exposure

The extent of IMP exposure will be assessed by the duration of IMP exposure.

Duration of IMP exposure is defined as last dose date – first dose date + 14 days, regardless of unplanned intermittent discontinuations (see Section 2.5.3 for calculation in case of missing or incomplete data). Duration of IMP exposure will be summarized descriptively as a quantitative variable (number, mean, SD, median, minimum, and maximum). In addition, duration of treatment exposure will also be summarized categorically by numbers and percentages for each of the following categories and cumulatively according to these categories:

- >0 and \leq 2 weeks
- >2 and \leq 4 weeks
- >4 and \leq 8 weeks
- >8 and \leq 12 weeks
- >12 and \leq 16 weeks
- ...
- ...
- >48 and \leq 52 weeks
- >52 weeks and \leq 52 weeks + 3 days
- > 52 weeks + 3 days

Additionally, the cumulative duration of treatment exposure will be provided, defined as the sum of the duration of treatment exposure for all patients, and will be expressed in patient years.

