Analysis of all treatment-emergent adverse event(s) leading to treatment discontinuation

- All treatment-emergent adverse events leading to treatment discontinuation, by primary SOC, HLG, HLT, and PT, showing the number (%) of patients sorted by the internationally agreed SOC order. The other levels (HLG, HLT, PT) will be presented in alphabetical order
- All treatment-emergent adverse events leading to permanent treatment discontinuation or drug interruption, by primary SOC and PT, showing number (%) of patients with at least one TEAE, will be presented by SOC internationally agreed order and by decreasing incidence of PTs within each SOC in the 300 q2w treatment group.

Analysis of Major Cardiovascular Adverse Events (MACE)

- The number and percentage (%) of patients with any treatment-emergent event selected for adjudication will be summarized by primary SOC and PT.
- All events submitted for adjudication will be listed, including the final adjudicated result.
- The number and percentage (%) of patients experiencing a treatment-emergent adjudicated event will be summarized within each treatment group.

- The risk difference (asymptotic 95% CI with continuity correction) will be computed for the dupilumab dose versus placebo. Kaplan-Meier plots to depict the course of onset over time will also be provided.

Analysis of adverse events of special interests (AESI) and other selected AE groupings

- All treatment-emergent adverse events, by selected standardized MedDRA query (SMQ) and PT or by laboratory values (as in ALT elevation), showing the number (%) of patients with at least 1 PT, sorted by decreasing incidence of PTs within each SMQ in the 300 q2w treatment group.
- For each AESI and other selected AE groupings,
 - Number (%) of patients with any specific TEAE
 - Number (%) of patients with any specific serious AE (regardless of treatment emergent status)
 - Number (%) of patients with any specific treatment emergent serious AE
 - Number (%) of patients with any specific AE leading to death
 - Number (%) of patients with any specific TEAE leading to permanent study drug discontinuation
 - Number (%) of patients with any specific TEAE related to IMP reported by investigator
 - Number (%) of patients with any specific TEAE by maximum intensity, corrective treatment, and final outcome
 - Number of any specific TEAE adjusted by the exposure duration

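### The AESI event-count rate counts TEAEs to last dose + 98 days but divides by an exposure ending at last dose + 14 days: about 23% too high for a fully followed completer under a constant hazard

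*SAP*

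**What the plan says.** **Numerator.** Protocol 9.4.2 sets the TEAE period as the "time between the first administration of study medication to the last administration of the IMP + 98 days". SAP 2.1.4 agrees. It builds the period from the treatment epoch, which ends at last dose + 14 days, and the residual treatment epoch, the "time from the last administration of the IMP +15 days to the last administration of the IMP + 98 days".

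**Denominator.** For each AESI and other selected grouping, SAP 2.4.5.1 lists the "Number of any specific TEAE adjusted by the exposure duration" and gives no definition of that duration at that point. The definition is in SAP 2.4.3.1: "Duration of IMP exposure is defined as last dose date – first dose date + 14 days". Cumulative exposure is "defined as the sum of the duration of treatment exposure for all patients, and will be expressed in patient years".

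**The patient-count line.** The next line of SAP 2.4.5.1 adjusts the number of patients with a TEAE by a differently named quantity, exposure duration at risk. The SAP does not say where that time ends. Protocol Table 10 lists the "Number of patients with the TEAE per 100 patient-years", also without defining the patient-years.

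**Data cut-off.** Protocol 9.5 and SAP 4 base the final analysis on a lock at the last patient's Week 52 visit, or earlier study discontinuation. Later data go to an addendum.

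**The concern.** A rate per unit of time needs events and person-time from the same window. Here the event window runs 84 days past the exposure window (98 − 14). An event with onset in the residual epoch adds to the count, but the days in which it could have occurred do not add to the denominator. Nothing offsets this, so the error has one direction.

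What is at stake is the absolute level of the AESI event rates. If they are set beside rates computed on matched time, they will look too high for reasons unrelated to the drug. The relative excess is larger for patients who stop early, so unequal discontinuation between arms could also move the between-arm ratio somewhat.

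**Working it through.** The documents state no exposure-adjusted rate, so there is no plan figure to reproduce. The check is on person-time.

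**Which exposure duration is meant.** SAP 2.4.5.1 does not cross-refer to SAP 2.4.3.1, but two things tie them together. SAP 2.4.3.1 sends the reader to SAP 2.5.3 for missing data in this calculation, and SAP 2.5.3 there calls the quantity the exposure duration. The patient-count line adds the words at risk and the event-count line does not.

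**Inputs.** Last planned dose at Week 50, so L = 350 days from first to last dose (Protocol 1.3.1, footnote f). Exposure = L + 14 (SAP 2.4.3.1). TEAE window = L + 98 (SAP 2.1.4). As a check, 1 + 350 + 98 = Day 449, which is the Week 64 target day in the SAP's tables, so the whole residual window is scheduled follow-up.

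**Full follow-up, constant hazard.** Overstatement factor = (L + 98)/(L + 14).

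| Last dose | Exposure (days) | TEAE window (days) | Factor |
|---|---|---|---|
| Week 50 (completer) | 364 | 448 | 1.23 |
| Week 24 (L = 168) | 182 | 266 | 1.46 |
| Week 8 (L = 56) | 70 | 154 | 2.20 |

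**Effect of the lock.** If only r residual days are observed, the factor is (L + 14 + r)/(L + 14). A patient whose follow-up ends at last dose + 14 days has r = 0 and a factor of 1.00. For completers enrolled uniformly over T days, the mean of r at the lock is 84 × (1 − 42/T). T is not in the documents, so a range is shown.

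| Assumed enrolment | Mean r (days) | Factor |
|---|---|---|
| 6 months (182 days) | 64.6 | 1.178 |
| 12 months (365 days) | 74.3 | 1.204 |
| 24 months (730 days) | 79.2 | 1.217 |
| 36 months (1,095 days) | 80.8 | 1.222 |

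**Effect of discontinuation.** Assume 20% stop at times spread evenly over treatment and completers are fully followed. Mean exposure is 0.8 × 364 + 0.2 × 182 = 327.6 days.
- Discontinuers fully followed: (327.6 + 84)/327.6 = 1.256.
- None of their residual time observed: (327.6 + 0.8 × 84)/327.6 = 1.205.

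**Effect of the hazard.** If the residual-period hazard is h times the on-treatment hazard, a completer's factor is (364 + 84h)/364. This gives 1.00 at h = 0, 1.115 at h = 0.5 and 1.231 at h = 1.

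**Between arms.** Assume 5% of one arm and 20% of the other have their last dose at Week 8, the rest complete, and all are fully followed.
- 5% arm: exposure 0.95 × 364 + 0.05 × 70 = 349.3; factor 433.3/349.3 = 1.2405.
- 20% arm: exposure 0.80 × 364 + 0.20 × 70 = 305.2; factor 389.2/305.2 = 1.2752.
- Ratio of two truly equal rates: 1.2752/1.2405 = 1.03.

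**The case against.** The strongest reply is that the size is uncertain and the consequence modest. The lock removes residual time for late enrollees, and death or withdrawal removes more. A constant hazard is wrong for some AESIs in SAP Table 2. Injection site reactions and symptomatic overdose with IMP can hardly start when no injections are being given, so their inflation is near zero. For those events a denominator running to + 98 days would dilute the rate. Both arms use the same windows. SAP 2.4.5 calls the safety analysis essentially descriptive, and AESIs are also reported as counts and percentages, which do not use this denominator. Finally, SAP 2.4.5.1 does not itself say which exposure duration it means.

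Most of this stands as a limit on size and on which remedy suits which event. It does not remove the mismatch. The last point is weak, because SAP 2.5.3 uses exposure duration for the SAP 2.4.3.1 quantity and no other definition exists.

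Three stronger readings are tempting, and the documents do not support them.
- **A reader might take 23% as a minimum.** It is the full-follow-up value for a completer. The Week 52-based lock, death and withdrawal can all bring the factor below it.
- **A reader might extend the error to every AESI rate.** The patient-count line uses a different term that may already be matched to the TEAE window. Together with the Protocol Table 10 rate, it is undefined rather than shown to be wrong.
- **A reader might quote a sevenfold error from a one-dose patient** (98/14 = 7.0). That is one patient's person-time; no such rate is reported.

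**Conclusion.** The mismatch is real for the event-count line in SAP 2.4.5.1. Followed as written, the plan counts up to 84 days of events per patient without the matching time.

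The overstatement is about 23% for a completer if the hazard is constant and the residual window is fully observed, and more for early discontinuers who are followed. At the planned lock it is about 18 to 22% for completers, given a constant hazard and uniform enrolment over an assumed 6 to 36 months. It falls if events are rarer off treatment, and is near zero for injection-linked events. The between-arm ratio shifts by about 3% in the assumed example of unequal stopping, and little otherwise.

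This affects absolute rates in a descriptive safety table, not the efficacy conclusions. It should be corrected before lock because it is a clear specification error and cheap to remove.

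**What to change.** In SAP 2.4.5.1:

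1. For the event-count line, define the denominator as observed time in the TEAE period: first dose to the earliest of last dose + 98 days, death, study withdrawal, end of study or data cut-off.
2. Alternatively, keep IMP exposure as the denominator and count only events in the treatment epoch (to last dose + 14 days). This may suit injection-linked events better. State in advance which rule applies to which AESI.
3. For the patient-count line, define exposure duration at risk as the same observed TEAE time, censored at the patient's first event. State that this is the denominator for the patient-years rate in Protocol Table 10.

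The cost is SAP wording and one derived variable, with no new data. Reported rates will be somewhat lower. For a fully followed completer, changing the denominator lowers the rate by 1 − 364/448 = 18.8%.

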2.4.5.2 Deaths

The following summaries of deaths will be generated for the safety population.

- Number (%) of patients who died by study period (TEAE, on-study, on-treatment, poststudy)
- Deaths in nonrandomized patients or randomized but not treated patients
- Treatment-emergent adverse events leading to death (death as an outcome on the adverse event case report form page as reported by the Investigator) by primary SOC, HLGT, HLT, and PT showing number (%) of patients sorted by internationally agreed SOC order, with HLGT, HLT, and PT presented in alphabetical order within each SOC.
- All pretreatment adverse events leading to death by primary SOC and PT, showing the number (%) of patients, sorted by the internationally agreed SOC order and decreasing incidence of PTs within each SOC.

A listing of deaths will be provided.

2.4.5.3 Analyses of laboratory variables

The summary statistics (including number, mean, median, Q1, Q3, standard deviation, minimum and maximum) of all laboratory variables (central laboratory values and changes from baseline) will be calculated for each visit or study assessment (baseline, each postbaseline time point, last on-treatment and/or worst on-treatment value) by treatment group. For each continuous parameters listed in [Section 2.1.4.3](#), mean changes from baseline with the corresponding standard error will be plotted over time in each treatment group. This section will be organized by biological function as specified in [Section 2.1.4.3](#).

The incidence of PCSAs (list provided in Appendix A) at any time during the treatment-emergent adverse event period will be summarized by biological function and treatment group whatever the baseline level and/or according to the following baseline status categories:

- Normal/missing
- Abnormal according to PCSA criterion or criteria

For parameters for which no PCSA criteria are defined, similar table(s) using the normal range will be provided.

For PCSA analyses, the laboratory measurements obtained at either scheduled or unscheduled visits should be used; and, both the centralized and local test results should be used, as long as their available dates/time is different from each other's. Centralized data will be used preferentially to the local measures in the PCSA analyses when measurements are performed on the same date and at the same time for a given laboratory test.

Possible Drug-induced liver injury

The liver function tests, namely AST, ALT, alkaline phosphatase, and total bilirubin, are used to assess possible drug-induced liver toxicity. The proportion of patients with PCSA values at any postbaseline visit by baseline status will be displayed by treatment group for each parameter. The proportion of patients with PCSA values at any postbaseline visit will also be displayed by duration of exposure for each treatment group.

Time to onset of the initial ALT and AST elevation (>3 x ULN) and total bilirubin elevation (>2 x ULN) (time to first observation of ALT >3 x ULN or total bilirubin >2 x ULN, whichever comes first) will be analyzed using Kaplan-Meier estimates, presented by treatment group. Consideration should be given to the impact of the spacing of scheduled tests. A graph of distribution of peak values of ALT versus peak values of total bilirubin will also be presented. Note that the ALT and total bilirubin values are presented on a logarithmic scale. The graph will be divided into 4 quadrants with a vertical line corresponding to 3 x ULN for ALT and a horizontal line corresponding to 2 x ULN for total bilirubin.

Listing of possible Hy's law cases identified by treatment group (eg, patients with any elevated ALT >3 x ULN, and associated with an increase in bilirubin ≥ 2 x ULN) with ALT, AST, alkaline phosphatase, total bilirubin, and the following complementary parameters: conjugated bilirubin and creatine phosphokinase, serum creatinine, complete blood count, HCV RNA.

Summarize the normalization by parameter (to ≤ 1 x ULN or return to baseline) of elevated liver function tests by categories of elevation (3 x, 5 x, 10 x, 20 x ULN for ALT and AST, 1.5 x ULN for alkaline phosphatase, and 1.5 x and 2 x ULN for total bilirubin), with the following categories of normalization: never normalized, normalized despite treatment continuation of IMP, or normalized after IMP discontinuation. Note that a patient will be counted only under the maximum elevation category.

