2.4.5 Analyses of safety data

The summary of safety results will be presented by treatment group.

General common rules

All safety analyses will be performed on the safety population as defined in [Section 2.3.2](#), unless otherwise specified, using the following common rules:

- The baseline value is defined as the last available value before the first dose of IMP.
- The potentially clinically significant abnormality (PCSA) values are defined as abnormal values considered medically important by the Sponsor according to predefined criteria/thresholds based on literature review and defined by the Sponsor for clinical laboratory tests and vital signs and ECG [Appendix A]
- PCSA criteria will determine which patients had at least 1 PCSA during the treatment-emergent adverse event period, taking into account all evaluations performed during the treatment-emergent adverse event period, including nonscheduled or repeated evaluations. The number of all such patients will be the numerator for the on-treatment PCSA percentage
- The treatment-emergent PCSA denominator by group for a given parameter will be based on the number of patients assessed for that given parameter in the treatment-emergent adverse event period by treatment group on the safety population.
- For quantitative safety parameters based on central laboratory/reading measurements, descriptive statistics will be used to summarize results and change from baseline values by visit and treatment group. Summaries will include the endpoint value and/or the worst on-treatment value. The endpoint value is commonly defined as the value collected at the end of treatment. If this value is missing, this endpoint value will be the closest value prior to the end of treatment epoch. The worst value is defined as the nadir and /or the peak post-baseline (up to the end of treatment epoch or EOT) according to the direction (minimum or maximum) of the abnormality as defined in the PCSA list
- The analysis of the safety variables will be essentially descriptive and no systematic testing is planned. Relative risks versus placebo and their 95% confidence intervals may be provided, if relevant
- All safety values including unscheduled measurements will be assigned to the appropriate safety analysis visit window defined in [Section 2.5.3](#).

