Appendix A Potentially clinically significant abnormalities criteria

CRITERIA for POTENTIALLY CLINICALLY SIGNIFICANT ABNORMALITIES for phase 2/3 studies (From BTD-009536 – 21-MAY-2014)

Parameter	PCSA	Comments
Clinical Chemistry		
ALT	By distribution analysis : >3 ULN >5 ULN >10 ULN >20 ULN	Enzymes activities must be expressed in ULN, not in IU/L. Concept paper on DILI – FDA draft Guidance Oct 2007. Internal DILI WG Oct 2008. Categories are cumulative. First row is mandatory. Rows following one mentioning zero can be deleted.
AST	By distribution analysis : >3 ULN >5 ULN >10 ULN >20 ULN	Enzymes activities must be expressed in ULN, not in IU/L. Concept paper on DILI – FDA draft Guidance Oct 2007. Internal DILI WG Oct 2008. Categories are cumulative. First row is mandatory. Rows following one mentioning zero can be deleted.
Alkaline Phosphatase	>1.5 ULN	Enzymes activities must be expressed in ULN, not in IU/L. Concept paper on DILI – FDA draft Guidance Oct 2007. Internal DILI WG Oct 2008.
Total Bilirubin	>1.5 ULN >2 ULN	Must be expressed in ULN, not in µmol/L or mg/L. Categories are cumulative. Concept paper on DILI – FDA draft Guidance Oct 2007. Internal DILI WG Oct 2008.
Conjugated Bilirubin	>35% Total Bilirubin and TBILI>1.5 ULN	Conjugated bilirubin dosed on a case-by-case basis.
ALT and Total Bilirubin	ALT>3 ULN and TBILI>2 ULN	Concept paper on DILI – FDA draft Guidance Oct 2007. Internal DILI WG Oct 2008. To be counted within a same treatment phase, whatever the interval between measurement.
CPK	>3 ULN >10 ULN	FDA Feb 2005. Am J Cardiol April 2006. Categories are cumulative. First row is mandatory. Rows following one mentioning zero can be deleted.

CRITERIA for POTENTIALLY CLINICALLY SIGNIFICANT ABNORMALITIES
for phase 2/3 studies
(From BTD-009536 – 21-MAY-2014)

Parameter	PCSA	Comments
CLcr (mL/min) (Estimated creatinine clearance based on the Cockcroft-Gault equation)	<15 (end stage renal disease)	FDA draft Guidance 2010
	≥15 - <30 (severe decrease in GFR)	Pharmacokinetics in patients with impaired renal function-study design, data analysis, and impact on dosing and labeling
	≥30 - < 60 (moderate decrease in GFR)	
	≥60 - <90 (mild decrease in GFR)	
≥ 90 (normal GFR)		
eGFR (mL/min/1.73m ²) (Estimate of GFR based on an MDRD equation)	<15 (end stage renal disease)	FDA draft Guidance 2010
	≥15 - <30 (severe decrease in GFR)	Pharmacokinetics in patients with impaired renal function-study design, data analysis, and impact on dosing and labeling

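### The liver time-to-onset analysis is named for ALT, AST and bilirubin, but its event definition leaves out AST

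*SAP*

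**What the plan says.** The part of SAP section 2.4.5.3 on possible drug-induced liver injury opens by setting its scope: "The liver function tests, namely AST, ALT, alkaline phosphatase, and total bilirubin, are used to assess possible drug-induced liver toxicity". AST is one of the four tests.

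The time-to-event sentence begins "Time to onset of the initial ALT and AST elevation (>3 x ULN) and total bilirubin elevation (>2 x ULN"). A parenthesis then turns that name into an operational rule: "time to first observation of ALT >3 x ULN or total bilirubin >2 x ULN, whichever comes first". The result "will be analyzed using Kaplan-Meier estimates, presented by treatment group".

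The same section also deals with AST in two other places. By-parameter tables of potentially clinically significant abnormalities (PCSA) are planned: "The proportion of patients with PCSA values at any postbaseline visit by baseline status will be displayed by treatment group for each parameter". A summary of whether raised values return to normal uses the categories "3 x, 5 x, 10 x, 20 x ULN for ALT and AST". Appendix A gives AST the same PCSA cut-offs as ALT. On the status of all this, SAP section 2.4.5 says: "The analysis of the safety variables will be essentially descriptive and no systematic testing is planned".

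**The concern.** A programmer works from the operational definition, not from the name. Under this definition the output would carry a title that covers AST while the event rule ignores it. A reader of the study report would take a flat stretch of the curve to mean that no AST elevation had occurred, which the analysis cannot show.

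The sentence is also unclear on a second matter. Its opening can be read as elevations taken parameter by parameter, whereas the parenthesis sets a single clock that starts at the first of two criteria. Two competent programmers could therefore produce different curves, and the choice would be made after the data were in hand. On a single clock, onset driven by bilirubin cannot be told apart from onset driven by a transaminase.

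**Working it through.** The plan attaches no event rate, hazard ratio, power or alpha to this analysis, so there is no stated figure to reproduce. The check compares the name with the rule.

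**Event status.** Take the three yes/no criteria: ALT >3 x ULN, AST >3 x ULN, total bilirubin >2 x ULN. They give 2 x 2 x 2 = 8 patterns. Compare an any-of-three event (the composite reading of the name) with the ALT-or-bilirubin event (the parenthesis).

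| ALT | AST | Bilirubin | Any of three | ALT or bilirubin | Difference |
|---|---|---|---|---|---|
| no | no | no | no event | no event | none |
| yes | no | no | event | event | none |
| no | no | yes | event | event | none |
| yes | no | yes | event | event | none |
| no | yes | no | event | **no event** | status |
| yes | yes | no | event | event | date, if AST is first |
| no | yes | yes | event | event | date, if AST is first |
| yes | yes | yes | event | event | date, if AST is first |

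Seven of the eight patterns keep their status. The AST-only pattern moves from event to censored. In three more, onset is dated late whenever AST crosses its limit before the others.

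If the name is instead read parameter by parameter, the mismatch on AST is the same, because no AST curve would exist. A bilirubin-only patient would then belong on the bilirubin curve alone.

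**Size of the dating error.** SAP section 2.1.4.3 schedules post-baseline laboratory samples at Weeks 4, 8, 12, 24, 36, 52 and 64. On scheduled samples, an AST-first patient is dated at least one interval late: 4 weeks between Weeks 4 and 12, 12 weeks between Weeks 12 and 36, 16 weeks between Weeks 36 and 52. For example, with AST above its limit at Week 4 and ALT above its limit at Week 24, the rule gives onset at Week 24, which is 24 - 4 = 20 weeks late. Unscheduled samples could shorten the gap. If the criteria are met in the same sample there is no error.

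**Size of the missing events.** The documents give no AST-only incidence. Assuming all 462 planned patients per arm are treated and followed, each AST-only patient is 100/462 = 0.22 percentage points of cumulative incidence. One such patient in an arm lowers its curve by 0.22 points, and five by 5 x 100/462 = 1.08 points. These counts are illustrations, not forecasts.

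**The case against.** The strongest reply is that this is a wording slip in one descriptive display and that AST is well covered elsewhere. That is largely right, and it rules out several stronger readings.

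- **That AST-only cases go uncounted in the trial.** They do not. The PCSA tables show each parameter by arm and baseline status, and again by duration of exposure. The normalization summary has AST categories, and the Hy's law listing displays AST values. The omission applies to this Kaplan-Meier analysis only.
- **That isolated bilirubin rises are passed off as onset of transaminase elevation.** The sentence names bilirubin openly as part of the analysis. What can fairly be said is that one composite curve cannot separate the two.
- **That this is the only time-to-event liver analysis.** SAP Table 2 makes drug-related hepatic disorder an adverse event of special interest, and SAP section 2.4.5.1 allows Kaplan-Meier displays for such events if they are numerous enough. Protocol section 8.3.1 lists significant ALT elevation, and protocol Table 10 plans Kaplan-Meier estimates for each type of special-interest event. Those rest on coded events or higher ALT limits, so they do not replace this display.
- **That adding bilirubin hides an ALT signal.** Assume 52-week ALT incidences of 1% on placebo and 2% on dupilumab, independent bilirubin elevations equally common in both arms, and composite risk a + b - ab. With b = 0.5% the risks are 1.495% and 2.49%; with b = 2% they are 2.98% and 3.96%. The ratio falls from 2.0 to 1.67 or 1.33, but the difference between arms stays near 1 point (0.995 and 0.98). Kaplan-Meier curves show absolute incidence, and the sentence specifies no ratio. The incidences are also assumed.
- **That listing and table disagree on bilirubin.** The Hy's law listing uses at or above 2 x ULN, while Appendix A uses "ALT>3 ULN and TBILI>2 ULN". This matters only for a value exactly at 2 x ULN, in a listing whose criterion is given as an example, and it can only add a case.

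After these concessions the mismatch on AST itself remains. None of the other displays supplies an onset time for an AST rise above 3 x ULN.

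**Conclusion.** The point holds as a low-severity mismatch within one sentence. The liver time-to-onset analysis is presented as covering AST, but its event rule does not, so AST-only patients are censored and AST-first patients are dated late in that display. This rests on following the parenthesis literally, which is the natural reading because it is the only operational definition given. The size depends on how many AST-only or AST-first patients occur, which the documents do not let us estimate. Safety analyses are descriptive, so the primary result, alpha, power and sample size are unaffected. The plan does not leave AST unexamined, and a reader should not infer that from this sentence.

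**What to change.** In SAP section 2.4.5.3, add AST >3 x ULN to the parenthesis as a third qualifying criterion, so that onset is the earliest of ALT >3 x ULN, AST >3 x ULN and total bilirubin >2 x ULN. State in the same place that this event is a composite. Show a curve for ALT or AST >3 x ULN separately from bilirubin, so that onset of transaminase elevation can be read directly. A full set of separate ALT, AST and bilirubin curves is an optional extra and is not needed to cure the mismatch.

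The cost is one SAP sentence and one or two additional curves. AST is already in the scheduled chemistry panel, so no new data are required. The change should be made before unblinding, so that the event definition is not chosen with results in view.
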